### 7.3 RATIONALE FOR FOSTAMATINIB

Fostamatinib is a tyrosine kinase inhibitor with activity against spleen tyrosine kinase (SYK). It has approved for the treatment of thrombocytopenia in adult patients with chronic immune thrombocytopenia (ITP). Studies of severe acute respiratory syndrome (SARS), induced by a related coronavirus, suggest that pathogenesis relies on a series of SYK-dependent events. SYK activity mediates cytokine and chemokine release induced by the activation of C-type lectin receptors (CLR) and immunoglobulin Fc receptors (FcR) resulting in neutrophil and monocyte lung ingress, sequential activation of neutrophil extracellular traps and the activation of lung epithelium and multiple myeloid cell. This is followed by inflammation and tissue destruction that contribute to ARDS. Fostamatinib, by inhibiting SYK activity, can block the production and release of cytokines induced via CLR and FcR activation, thus potentially ameliorating the cytokine storm that often precedes ARDS.

Fostamatinib is the only SYK inhibitor approved for clinical use, offering a distinct anti-inflammatory potential with a proven safety profile. Moreover, its anti-inflammatory effect is specific as preclinical toxicity studies showed that SYK inhibition with fostamatinib did not adversely affect innate immune responses in three

MATIS version 4.0 dated 2nd November 2022

IRAS: 282552 Page **33** of **57** 

different host resistance models, which is consistent with its clinical safety profile

#### 7.4 ADMINISTRATION OF FOSTAMATINIB

#### Administration

For subjects who become unable to receive fostamatinib treatment orally (e.g, intubated subjects), tablets can be crushed until granular with an approximate particle size <2 mm (based on the diameter of an NG tube), added to approximately 10 mL of water (or suitable volume for administration through a feeding tube), and stirred to mix before administration through an enteral feeding tube. The tablet is not expected to be fully dissolved prior to administration.

#### **Caveats**

The safety and efficacy of fostamatinib was evaluated using intact tablets only, so we do not have specific safety or efficacy data to support crushing tablets and administering through an NG tube. However, we have internal data on file that supports the stability of the crushed tablet for approximately 24 hours in a slightly basic pH (e.g. sterile water).

#### **Crushing tablets**

Based on findings from animal studies and the mechanism of action, fostamatinib can cause fetal harm when administered to a pregnant woman. Therefore, it is recommended that appropriate precautions should be followed during preparation of the crushed tablets: the tablets should be crushed and solubilized in water within a hood, and the individual preparing the crushed tablet wear gloves and a particle mask.

#### 7.5 DOSE MODIFICATIONS FOR FOSTAMATINIB

**Table 4. Dose Adjustments for Fostamatinib** 

Hypertension	Recommended Action
Stage 1: systolic between 130-139 or diastolic between 80-89 mmHg	
 
Monitor, or initiate or increase dosage of antihypertensive medication for subjects with increased cardiovascular risk and adjust as needed until BP is controlled, in accordance with local standards.
 

Stage 2: systolic at least 140 or diastolic at least 90 mmHg	
 
Initiate or increase dosage of antihypertensive medication and adjust as needed until BP is controlled.
 

MATIS version 4.0 dated 2nd November 2022

IRAS: 282552 Page **34** of **57** 

Hypertensive crisis: systolic
over 180 and/or diastolic
over 120 mmHg

- Interrupt or discontinue study drug.
- Initiate or increase dosage of antihypertensive medication and adjust as needed until BP is controlled. If BP returns to less than the target BP, resume study drug at same daily dose.

Toxicity	Recommended Action
AST/ALT is 5 x ULN or higher and total BL is less than 2 x ULN	
 
Interrupt study drug.
 
Recheck LFTs every 72 hours:
 
If AST and ALT decrease, recheck until ALT and AST are no longer elevated (below 1.5xULN) and total BL remains less than 2xULN; resume study drug at next lower daily dose.
 
If AST/ALT persist at 5xULN or higher for 2 weeks or more, discontinue study drug.
 

AST/ALT is 3 x ULN or higher and less than 5 x ULN	
 
If patient is symptomatic (e.g., nausea, vomiting, abdominal pain):         
 
Interrupt study drug.
 
Recheck LFTs every 72 hours until ALT/AST values areno longer elevated (below 1.5 x ULN) and total BL remains less than 2 x ULN.
 
Resume study drug at next lower daily dose.
 
 
 

	If patient is asymptomatic:
	
 
Recheck LFTs every 72 hours until ALT/AST <1.5 x ULN) and total BL remains less than 2xULN.
 
Consider interruption or dose reduction of study drug if ALT/AST and TBL remain in this category (AST/ALT is 3 to 5 x ULN; and total BL remains less than 2 x ULN).
 
If interrupted, resume study drug at next lower daily dose when ALT/AST are no longer elevated (<1.5xULN) and total BL remains <2 x ULN.
 
If AST/ALT persist at 5 x ULN or higher for 2 weeks or more, discontinue study drug.
 

AST/ALT is 3 x ULN or higher and total BL >2 x ULN	
 
Check direct and indirect BL levels. If direct BL is >2x ULN then discontinue study drug, if only indirect BL is >2x ULN then monitor as above.
 

Elevated unconjugated (indirect) BL in absence of other LFT abnormalities	
 
Continue study drug with frequent monitoring since isolated increase in unconjugated (indirect) BL may be due to UGT1A1 inhibition or the underlying disease.
 

Diarrhoea	
 
Manage diarrhoea using supportive measures (e.g., dietary changes, hydration and/or antidiarrheal medication) early after the onset until symptom(s) have resolved.
 
If symptom(s) become severe (Grade 3 or above), temporarily interrupt study drug.
 

MATIS version 4.0 dated 2nd November 2022

IRAS: 282552 Page **35** of **57** 

	
 
If diarrhoea improves to mild (Grade 1), resume study drug at the next lower daily dose.
 

Neutropenia	
 
If absolute neutrophil count decreases (ANC <1.0 x 109/L) (or is low at baseline) give G-CSF support to ensure NP> 1.0 x 109/L
 

#### 7.6 RATIONALE FOR RUXOLITINIB

JAK and STAT molecules are proteins that transduce extracellular stimulation into intracellular signalling, leading to expression of a host of inflammatory cytokines in a variety of immune cells (Elli et al., 2019). Ruxolitinib is a JAK1/JAK2 inhibitor approved for clinical use in the treatment of splenomegaly, myelofibrosis, polycythaemia vera and graft-versus-host disease. It is an oral agent with a rapid mode of action. Inhibition of STAT3 activation occurs within 2 hours of RUX administration and downregulates IL-6 and IL-23 signalling important for the proinflammatory effects of Th17 cells. Further, RUX administration leads to in reductions in serum levels TNFa and CRP. In addition, JAK2 inhibitors have been shown to block receptor-mediated endocytosis, thereby preventing viral cellular entry and assembly (Jagasia et al., 2020).

#### 7.7 DOSE MODIFICATIONS FOR RUXOLITINIB

#### End stage renal failure patients

Patients with glomerular filtration rate (GFR) <15 ml/min (dialysis and non-dialysis patients) will receive 20mg three times a week the first week and for the second week 10 mg three times a week (taken at the end of dialysis if on dialysis).

Patients with GFR ≥15 ml/min to < 30 ml/min, 5 mg twice a day for 1 week, then 5 mg once a day for 1 week.

For dialysis patients, pharmacokinetic (PK) levels will be assessed before each dialysis and at Day 14 and Day 28.

Ruxolitinib dose for these patients will be assessed after 10 dialysis patients complete these doses to Day 14.

#### Dose reductions

Dose reductions or interruptions for non-haematological toxicity attributed to ruxolitinib are permitted in order to allow the patient to continue on the study. For haematological toxicity, the counts should be supported with blood product support ensuring that the platelet count remains  $> 50 \times 109$ /L. The dose of ruxolitinib may be reduced in response to certain toxicities as detailed below. Doses of supportive medications should be adjusted

according to standard practice. If absolute neutrophil count decreases (ANC  $<1.0 \times 109/L$ ) (or is low at baseline) give G-CSF support to ensure NP>  $1.0 \times 109/L$ 

Table 5. Management of decline in haematologic parameters

Parameter(s) at Time of Decline	Action
PLT < 50 x 10  /L	Transfuse platelets to ensure >50 x 109/L
ANC < 1.0 x 10  /L	Support with G-CSF to ensure NP> 1.0 x 109/L

In response to a decline in renal function (eGFR < 30ml/min) OR hepatic function (AST/ALT > 1.5 x ULN), the dose should be reduced by 50%, to be administered twice daily and patients should be carefully monitored. The dose can be re-escalated if eGFR subsequently increases above 30ml/min OR AST/ALT decreases to < 1.5 x ULN as applicable.

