## 7 TREATMENT

It is accepted that SOC may change during a rapidly evolving pandemic. Co-enrolment to other trials and rescue therapy, either pre- or post-randomisation, is permitted and will be accounted for in the statistical analysis.

Table 2. Ruxolitinib (RUX)

Period	Dose	Frequency
Day 1-7	10mg	Twice daily
Day 8-14	5mg	Twice daily

Table 3. Fostamatinib (FOS)

Period	Dose	Frequency
Day 1-7	150mg	Twice daily

MATIS version 4.0 dated 2nd November 2022

IRAS: 282552 Page **32** of **57** 

Day 8-14 100mg Twice daily	
----------------------------	--

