# 7.15 SUPPLY OF STUDY TREATMENT

Ruxolitinib will be provided free of charge by Novartis at the following strengths: 5 mg, 10 mg, and 20 mg. Each tablet contains 5 mg, 10mg, or 20mg ruxolitinib (as phosphate). The tablets should not be stored above 30°C. PVC/PCTFE/Aluminium blister packs containing 14 or 56 tablets or multipacks containing 168 (3 packs of 56) tablets.

Fostamatinib will be provided free of charge by Rigel at the following strengths: 100 mg and 150 mg. Each film-coated tablet contains either 126.2 mg or 189.3mg of fostamatinib disodium hexahydrate equivalent to 100 mg and 150mg of fostamatinib respectively. This medicinal product does not require any special temperature storage conditions. It should be stored in the original package to protect from moisture and keep the bottle tightly closed.

The local trial pharmacist will be responsible for maintaining and updating the drug accountability log in the MATIS pharmacy file which will be used to monitor compliance. All unfinished bottles will be returned to the trial pharmacist who will count and document any unused medication. All IMPs can then be destroyed in accordance with local pharmacy practice and this will be documented on the drug destruction log in the hospital pharmacy file

MATIS version 4.0 dated 2nd November 2022

IRAS: 282552 Page **39** of **57** 

Imperial College Healthcare

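### Protocol section 7.7 has two ruxolitinib renal rules with no stated boundary, so a participant whose eGFR falls below 15 on study fits two different regimens, one with a week 2 dose that whole supplied tablets cannot make

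*Protocol*

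**What the plan says.** The standard ruxolitinib schedule in protocol section 7, Table 2, is "Day 1-7 10mg Twice daily" followed by "Day 8-14 5mg Twice daily".

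Section 7.7 then changes the dose for renal function in two places.

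- **Banded rule.** Under the heading "End stage renal failure patients", participants with GFR below 15 ml/min, on dialysis or not, "will receive 20mg three times a week the first week and for the second week 10 mg three times a week". Those with GFR from 15 to below 30 ml/min get "5 mg twice a day for 1 week, then 5 mg once a day for 1 week". The text does not say whether the bands refer to GFR at entry, GFR on treatment, or both.
- **Reduction rule.** Under the heading on dose reductions, the trigger begins "In response to a decline in renal function (eGFR < 30ml/min" and has no lower limit. AST/ALT above 1.5 x ULN is an alternative trigger in the same sentence. The action is that "the dose should be reduced by 50%, to be administered twice daily and patients should be carefully monitored". Re-escalation is allowed if eGFR rises above 30 ml/min or AST/ALT falls below 1.5 x ULN. The banded rule has no such provision.

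No sentence gives one rule precedence, and none excludes participants under the banded rule from the reduction rule.

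On supply, section 7.15 states: "Ruxolitinib will be provided free of charge by Novartis at the following strengths: 5 mg, 10 mg, and 20 mg". The documents say nothing about splitting ruxolitinib tablets or about another formulation.

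**The concern.** A site treating a participant whose renal function worsens during the 14 days finds two instructions in one section. For some eGFR values they do not give the same regimen. Starting dialysis on study is foreseeable, because renal replacement therapy is a secondary endpoint. The banded rule addresses dialysis and the reduction rule does not.

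Two sites could follow the protocol faithfully and give different regimens to participants with the same renal function. Section 11.1 lists use in hepatic impairment and in moderate, severe or end stage renal failure among ruxolitinib's identified and potential risks, so this is a group in which the instruction should be unambiguous. Section 7.7 also plans to assess the dose after 10 dialysis patients have completed the banded doses to Day 14, which presupposes one defined regimen.

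The second issue is practical. Halving the week 2 dose gives a quantity smaller than the smallest tablet supplied.

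**Working it through.** No sample size, power or alpha figure is involved, and the plan gives no derived figure to reproduce. The check is dose arithmetic.

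**Inputs.** Standard dose: Table 2. Banded regimens and the 50% rule: section 7.7. Tablet strengths 5, 10 and 20 mg: section 7.15.

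**Step 1. Apply the reduction rule to the standard dose.**

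- Week 1: 0.5 x 10 mg = 5 mg twice daily; 5 x 14 = 70 mg a week.
- Week 2: 0.5 x 5 mg = 2.5 mg twice daily; 2.5 x 14 = 35 mg a week.
- Total: 70 + 35 = 105 mg.

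**Step 2. Compare with the banded rule, GFR below 15 ml/min.**

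| | Banded rule | Reduction rule |
|---|---|---|
| Week 1 single dose | 20 mg | 5 mg |
| Week 1 total | 20 x 3 = 60 mg | 70 mg |
| Week 2 single dose | 10 mg | 2.5 mg |
| Week 2 total | 10 x 3 = 30 mg | 35 mg |
| Administrations a week | 3 | 14 |
| 14-day total | 90 mg | 105 mg |

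The single dose differs by a factor of 20/5 = 10/2.5 = 4. The weekly total under the banded rule is 60/70 = 30/35 = 0.857 of the other, about 14% lower.

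**Step 3. Compare with the banded rule, GFR 15 to below 30 ml/min.**

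- Week 1: 5 mg twice daily under both (70 mg).
- Week 2: 5 mg once daily (35 mg) against 2.5 mg twice daily (35 mg).
- The totals agree at 105 mg. Only the week 2 single dose and frequency differ.

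**Step 4. Check the tablets.** 5 mg is one whole tablet. 2.5 mg is below the smallest strength, so no combination of whole 5, 10 and 20 mg tablets makes it. This does not depend on the renal conflict: the AST/ALT trigger gives the same 2.5 mg twice daily in week 2 from the standard dose.

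**Step 5. Apply the reduction rule to someone already on a banded regimen.**

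- GFR below 15, with AST/ALT rising above 1.5 x ULN: an instruction to halve the dose and give it twice daily does not fit a regimen given three times a week.
- GFR 15 to below 30, with a further fall inside the band: the banded rule leaves the regimen as it is. The reduction rule, read literally, halves it, giving 2.5 mg twice daily in week 1 and a daily total of 2.5 mg in week 2.

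**The case against.** The strongest reply is that the two rules have different scopes. The banded text reads like a full two-week course assigned to someone who already has that GFR. The other text sits under dose reductions, is framed as a response to toxicity, is triggered by a decline and allows re-escalation. On that reading one rule is a starting regimen and the other an on-treatment response.

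This is a plausible account of the intent, and it narrows the point to an unstated boundary. It does not remove it. The banded text never mentions entry or baseline. The reduction trigger has no lower limit, so a participant falling below 15 ml/min on study meets both conditions. Step 5 shows that participants who enter on a banded regimen can also meet the reduction trigger.

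Three further objections limit what can be claimed, and each is right.

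- A reader might infer that total exposure differs for everyone with eGFR below 30. It does not: from the standard dose, the totals agree between 15 and 30 ml/min. The factor of four below 15 compares single doses on schedules of different frequency. The weekly totals differ by about 14%.
- A reader might infer that the 2.5 mg dose cannot be given at all. The documents support only that whole tablets cannot make it. Whether splitting is acceptable is not addressed.
- A reader might infer that the ambiguity turns compliers into non-compliers, since full banded dosing scored against the reduction rule is 60/70 = 86%, under the SAP's 90% threshold. That needs someone prescribed under one rule and scored under the other, and no passage directs this. The natural reading of SAP section 3.1.2 is that each participant is measured against what was prescribed for them, and section 2.6 refers to SAP I, which is not among the documents. The analyses concerned are the stage 1 per-protocol analysis and the exploratory complier analysis in section 3.1.5. The latter is also run at 60%, 70% and 80%, where 86% passes.

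**Conclusion.** The inconsistency is real but narrower than it may look. Its main weight is below 15 ml/min on study, where both rules can apply and they differ in single dose, frequency and weekly total. At 15 to below 30 ml/min, from the standard dose, it comes down to the week 2 schedule. Separately, the 50% rule yields 2.5 mg in week 2 through either its renal or its hepatic trigger, which the listed strengths cannot supply as whole tablets. Its twice-daily wording also does not fit the three-times-weekly regimen.

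This rests on reading section 7.7 as written, with the halving applied to the Table 2 dose unless stated otherwise. The documents give no count of participants likely to be affected. The intention-to-treat primary analysis and the sample size do not depend on the point. It is a matter of consistent dosing and safety, and of a clear definition of prescribed dose in the adherence analyses. No view is taken on which regimen is right.

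**What to change.** The sponsor's clinical and pharmacy team should reconcile the two parts of section 7.7 with each other and with section 7.15. The revised text should state:

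- which rule applies when a participant meets both;
- what happens when a participant already on a banded regimen meets a renal or hepatic reduction trigger;
- how each resulting dose, in each week, is given with the supplied product.

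The SAP should then add one sentence saying that the prescribed dose in the adherence calculation (section 3.1.2) and in the complier definition (section 3.1.5) is the dose under the reconciled rule.

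The cost is a wording amendment to section 7.7 and that SAP sentence. No extra participants or procedures are needed.

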# Potential for Ruxolitinib-induced liver injury

Participants with transaminase increase combined with total bilirubin increase may be indicative of potentially severe ruxolitinib-induced liver injury and should be considered as clinically important events and assessed appropriately to establish the diagnosis. The required clinical information, as detailed below, should be sought to obtain the medical diagnosis of the most likely cause of the observed laboratory abnormalities.

The threshold for potential ruxolitinib-induced liver injury may depend on the participant's baseline AST/ALT and total bilirubin value; participants meeting any of the following will require further follow-up:

- For participants with normal ALT and AST and total bilirubin value at baseline: AST or ALT > 3.0 x ULN combined with total bilirubin > 2.0 x ULN
- For participants with elevated AST or ALT or total bilirubin value at baseline: (AST or ALT > 2 x baseline or AST or ALT >300 U/L) whichever occurs first combined with (total bilirubin > 2 x baseline AND > 2.0 x ULN)

Other causes of abnormal liver tests should also be considered, and their role clarified before ruxolitinib is assumed as the cause of liver injury. A detailed history, including relevant information such as review of ethanol consumption, concomitant medications, herbal remedies, supplement consumption, history of any pre-existing liver conditions or risk factors, should be collected. Laboratory tests to be done include ALT, AST, total bilirubin, direct and indirect bilirubin, GGT, LDH, prothrombin time (PT)/INR, alkaline phosphatase, albumin, and creatine kinase.

Imperial College Healthcare

#### 7.8 TREATMENT RECOMMENDATIONS FOR OTHER ADVERSE EVENTS

Grade 1 or 2: maintain dose level

Grade 3: Reduce dose level 50% until resolved to ≤ Grade 2

Grade 4: Hold dose and then discontinue from study

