#### 7.16 TREATMENT DURATION

The planned duration of treatment is 14 days. Participants may be discontinued from treatment earlier due to unacceptable toxicity or disease progression which will be recorded as Serious Adverse Event (SAE). If participant is being discharged prior to day 14 they will go home and continue with the treatment plan.

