# 9 ASSESSMENT AND FOLLOW-UP

# 9.1 COLLECTING FOLLOW-UP INFORMATION

The following information will be ascertained at the time of death or discharge or at 28 days after randomisation (whichever is sooner):

- Vital status (alive / dead, with date and presumed cause of death, if appropriate)
- Hospitalisation status (inpatient / discharged, with date of discharge, if appropriate)
- Use of ventilation (with days of use and type, if appropriate)
- Use of renal dialysis or haemofiltration

This information will be obtained and entered into the web-based IT system by a member of the hospital clinical or research staff. Follow-up information is to be collected on all study participants, irrespective of whether or not they complete the scheduled course of allocated study treatment. Study staff will seek follow-up information through various means including medical staff, reviewing information from medical notes, routine healthcare systems, and registries.

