#### 9.2 DURATION AND MODE OF FOLLOW-UP

All randomised participants are to be followed up until death, discharge from hospital or 28 days after randomisation (whichever is sooner). It is recognised that in the setting of this trial, there may be some variability in exactly how many days after randomisation, information on disease status is collected. This is acceptable and will be taken account of in the analyses and interpretation of results, the principle being that some information about post-randomisation disease status is better than none.

Where discharge occurs before 14 days, study medication will be sent home with patient. The study team will send a pre-paid envelope to the patients to return any unused medication and empty bottles if patients are not able to attend Day 14 and Day 28 visits in person.

Where discharge occurs before 28 days, patients will be invited to return weekly for monitoring of blood tests to confirm continued recovery from illness. Where this is not possible, monitoring of clinical status will be achieved by telephone.

Longer term (up to 10 years) follow-up will be sought through linkage to electronic healthcare records and medical databases including those held by NHS Digital, Public Health England and equivalent bodies, and to relevant research databases (e.g. UK Biobank, Genomics England).

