#### 12.4 WITHDRAWAL OF CONSENT

A decision by a participant that they no longer wish to continue receiving study treatment should **not** be considered to be a withdrawal of consent for follow-up. However, participants are free to withdraw consent for some or all aspects of the study at any time if they wish to do so. In accordance with regulatory guidance, deidentified data that have already been collected and incorporated in the study database will continue to be used (and any identifiable data will be destroyed).

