Every effort will be made to obtain follow-up data for all participants including those that stop treatment. The number and proportion of participants missing WHO COVID-19 status by treatment group and visit will be tabulated (see section 2.5 above). For participants who are discharged early the assumption will be made that they did not progress to grade 5 WHO scale. If there is a >5% rate of missing outcomes after this, we will impute missing WHO COVID-19 data in the primary analysis model using multiple imputation under the assumption of missing at random (MAR). That is the probability of being missing is not dependent on the values of unobserved data, conditional on the observed values of the variables included in the analysis model. Imputation under MAR using chained equations following the guidance of White et al. will be undertaken.⁴ Variables in the imputation model will include the variables in the primary analysis model described above plus baseline WHO COVID-19 score (3 or 4), age (<65 or ≥65), receipt of dexamethasone and/or tociluzimab at the time of or prior to randomisation into MATIS. Additional auxiliary variables that are suspected to be associated with the outcome and are predictors of missingness will also be included. These are receipt of any effective treatments post randomisation as a result of co-enrolment when occurring postrandomisation, and receipt of known effective treatments dexamethasone and tociluzimab postrandomisation (>1 day post randomisation) and WHO COVID-19 scores at day 1 and day 7. Using White et al.'s rule of thumb we will impute m datasets based on the percentage of participants with incomplete outcomes, where m will be rounded to the nearest 10, for example if 8% of participants have incomplete primary outcome then m=10 will be used.

Before undertaking the multiple imputation as described above we will impute any missing baseline data deterministically only using other baseline data, this includes the baseline WHO COVID-19 status, age, receipt of dexamethasone and/or tociluzimab at the time of or prior to randomisation into MATIS. To do this we will impute missing values with the mean values of observed data. In line with White et al., outcomes will be imputed separately for each treatment group.

Imputed datasets will then be analysed using the primary analysis model described above.

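### Protocol 7.8 takes patients off the study, not just off the drug, after a grade 4 event, which contradicts the follow-up rules in 9.1, 9.2 and the SAP

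*Protocol*

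**What the plan says.** Protocol 7.8 gives general treatment recommendations by grade: keep the dose at grades 1 and 2, halve it at grade 3, and at grade 4 "Grade 4: Hold dose and then discontinue from study". Section 8.3 defines grade 4 as life-threatening. Section 7.8 does not say that follow-up continues, and it does not point to section 9.

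The follow-up sections say the opposite:

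- Protocol 9.1: "Follow-up information is to be collected on all study participants, irrespective of whether or not they complete the scheduled course of allocated study treatment".
- Protocol 9.2 follows everyone randomised to death, discharge or day 28, whichever comes first.
- SAP 3.1.2: "Every effort will be made to obtain follow-up data for all participants including those that stop treatment".
- Protocol 12.4: a participant's own decision to stop treatment "should not be considered to be a withdrawal of consent for follow-up".

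Where the protocol deals with toxicity elsewhere, it separates drug from study. Table 4 has "If AST/ALT persist at 5xULN or higher for 2 weeks or more, discontinue study drug", and 7.16 has "Participants may be discontinued from treatment earlier due to unacceptable toxicity or disease progression".

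**The concern.** A site cannot obey both 7.8 as written and 9.2. Section 7.8 is where an investigator would look after a grade 4 event that Tables 4 and 5 do not cover, and it has no attribution condition, so the event need not be drug-related.

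The instruction acts on a study dose, and SOC has none. A literal reading therefore removes patients from RUX and FOS only. Two sets of data would be exposed:

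- **Day-14 primary outcome**, when the grade 4 event comes before the endpoint.
- **Day-28 non-fatal outcomes** (ventilation, renal replacement, thromboembolism). SAP 3.2.3 fits these on complete cases, with no imputation or sensitivity analysis.

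Loss confined to the drug arms, among patients whose risk may differ from the rest of their arm, can bias the comparison with SOC.

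**Working it through.** **1. The wording, side by side**

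| Place | What stops | Follow-up afterwards |
|---|---|---|
| Protocol 7.8, grade 4 | the study | not mentioned |
| Protocol Table 4 | study drug | not mentioned |
| Protocol 7.16 | treatment | not mentioned |
| Protocol 9.1 | scheduled treatment | continues |
| Protocol 9.2 | – | all randomised, to day 28 at most |
| Protocol 12.4 | treatment, by the participant's decision | continues unless consent for it is withdrawn |
| SAP 3.1.2 | treatment | continues |

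Only 7.8 ends participation. The heading of 7.8 and its other lines concern dose, so stopping the drug is the likely intent. Section 12.4 does not repair 7.8, because it covers a participant's choice and not a removal that the protocol directs.

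**2. The plan's own figures, as a baseline**

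Inputs (Protocol 3.1 and 4.1, SAP 1.5): 50% versus 30%; 57 and 152 per arm, including 5% for missing outcomes, so about 54 and 144 evaluable; one-sided 0.25 and 0.027. The pooled-variance normal approximation for two proportions gives:

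- Stage 1: Φ[(0.2 − 0.6745 × 0.0943)/0.0923] = 93.0% (stated 92%).
- Both stages, with correlation √(54/144) = 0.61: 89.4% (stated 90%).
- Two comparisons at 0.027 with correlation 0.5: family-wise error 4.9% (stated maximum 5%).

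The stated design reproduces, so 0.027 per comparison is a sound starting point.

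**3. Illustration for the day-14 outcome**

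From the plan: n = 152, 50% severe, z = 1.927 for one-sided 0.027. Assumed, because the documents give no grade 4 rate: 3 of 152 in one drug arm are lost before the endpoint, their true risk is r, the drug has no effect, and imputation recovers nothing.

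- Observed risk in the drug arm: q = (76 − 3r)/149.
- Log odds ratio against 50%: L = ln[q/(1 − q)].
- Standard error: √[1/(149q(1 − q)) + 1/(152 × 0.25)] = 0.231.
- One-sided error: Φ(−1.927 − L/0.231).

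| r | q | L | one-sided error |
|---|---|---|---|
| 0.4 | 74.8/149 = 0.502 | +0.008 | 0.025 |
| 0.5 | 74.5/149 = 0.500 | 0 | 0.027 |
| 0.6 | 74.2/149 = 0.498 | −0.008 | 0.029 |
| 0.8 | 73.6/149 = 0.494 | −0.024 | 0.034 |

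The sign depends only on whether those lost were at higher or lower risk than the rest of their arm.

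**4. Illustration for a day-28 non-fatal outcome**

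Assume a 20% rate in both arms, which is 30.4 events in 152, with 3 lost from the drug arm:

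- Risk 50% in those lost: (30.4 − 1.5)/149 = 19.4%, a false odds ratio of 0.96.
- Risk 10% in those lost: (30.4 − 0.3)/149 = 20.2%, a false odds ratio of 1.01.

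No imputation would offset this, because the analysis uses complete cases.

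**The case against.** The strongest reply is that the rest of the plan already answers the point. Section 9.1 is explicit. It lets outcomes be taken from notes, routine systems and registries, so even a patient taken off study visits can have outcomes recorded. Loss needs a chain: a grade 4 event with no rule of its own, occurring before the endpoint, handled literally, and not recovered from records. Many life-threatening respiratory events already meet the endpoint. Deaths are collected separately under 8.5. The final analysis imputes using day 1 and day 7 scores (SAP 3.1.2 and 3.1.3), and Protocol 4.2 plans a sensitivity analysis that relaxes missing at random. All of this stands, and it makes the effect small and conditional. It does not change what 7.8 tells a site to do.

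A reader might infer more than the documents support:

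- **That the trial is biased towards the drugs.** Nothing shows that any site read 7.8 literally, and the direction is unknown.
- **That the error nearly doubles.** If 5% of a drug arm (7.6 of 152) is lost at 80% risk, q = (0.5 − 0.04)/0.95 = 0.484 and the same formula gives 0.049. That uses the arm's whole 5% allowance for missing outcomes on this one group and assumes that imputation recovers nothing. At 40% risk the same loss gives 0.022.
- **That stage 1 is compromised.** Three lost from each drug arm is 6/171 = 3.5%, under the 5% trigger for imputation and the extreme-case analysis. With 3 of 57 lost, an ineffective arm's chance of passing would move from 0.25 to between 0.23 (risk 40%) and 0.31 (risk 80%). But three is an assumed number. The rule is non-binding (SAP 1.5.1), the monitoring committee reads the p-value as a continuous measure (Protocol 4.1), and withdrawal summaries are prepared at stage 1 (SAP 2.5).
- **That 7.7 has the same fault.** It allows dose reductions "in order to allow the patient to continue on the study". That wording is loose, but it removes nobody.

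**Conclusion.** The conflict is real and can be checked from the text alone. Protocol 7.8 says study where it almost certainly means drug, and no other sentence corrects it. The consequence is small and conditional. It arises only if a site puts 7.8 above 9.1 and also stops record-based data collection, and it is then confined to RUX and FOS.

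Under the assumed loss of 3 of 152, with true risk between 40% and 80% and no help from imputation, the one-sided error lies between 0.025 and 0.034 around the planned 0.027. A 20% day-28 outcome would show a false odds ratio between 0.96 and 1.01. These figures illustrate scale. They are not estimates, because the documents give neither a grade 4 rate nor the risk of those who would be removed.

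**What to change.** In Protocol 7.8, replace the grade 4 ending with: *discontinue study drug; continue all follow-up to day 28 under 9.1*. Tell sites of the change. For anyone already taken off study under 7.8 who did not withdraw consent, retrieve day-14 and day-28 status from the sources that 9.1 names. Section 7.7 needs no change.

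The cost is one phrase in a protocol amendment and a note to sites. The rule for stopping the drug is unchanged, and no patients, visits or data fields are added.
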